- (1) *Combining sites with low enrollment.* The SAP, section 3.C. states that for analyses that use sites as a stratification factor, sites with enrolling fewer than four subjects will be combined to form a single “super-site”. The sites affected are 016 (Ottawa) three subjects, 030 (Calgary) two subjects, 034 (IND) three subjects, 069 (PMDI), three subjects, 110 (UC Irvine), three subjects, 132 (LSU) three subjects, 139 (PHREI), two subjects, 305 (Alberta) three subjects, making a grand total of 22 subjects.

- (2) *Influence of Symptomatic Medication on the Primary Outcome.* Section 4C. III states that “Supplementary analyses of the final study outcome will be conducted with current use of symptomatic medication (levodopa equivalents) added as an additional predictor variable”. Since use of symptomatic medication is a post-randomization variable and may be determined in part by post-randomization values of the outcome variable, it should not be used as a predictor variable. Subjects who show a more rapid early decline may be more likely to receive symptomatic medication. This could result in an artefactual positive correlation between use of symptomatic medication and rapidity of disease progression which might distort the estimate of the randomized treatment. To avoid this artefact we will estimate the effect on the primary outcome of both current and cumulative dosages of symptomatic medication from a mixed model analysis using data from all study visits and which explicitly allows subjects to have differing underlying rates of disease progression. In essence this analysis uses each subject as his or her own control in estimating the influence of symptomatic medication on disease progression. It will be performed on the aggregate data from the final study data-base, prior to breaking the blind as to the randomized treatment. The estimated coefficients of the two LED variables (current and cumulative levodopa equivalent doses) will then be used to adjust each subject’s final UPDRS value to the projected value that the subject would have had if he or she had not received symptomatic medication. Since these projections will not use the randomized treatment, the treatment effect on the projected outcome variables can be estimated using the same model as the primary analysis, i.e. stratifying by site and including baseline UPDRS as a covariate. This analysis will have the correct alpha-level under the overall null hypothesis (no effect of isradipine relative to placebo on either disease progression or usage of symptomatic medication) irrespective of whether the relationship between these two outcome variables is modeled accurately. A member of the Steering Committee asked about the possible influence of body weight on the effect of LED. To assess this we conducted preliminary analyses on the aggregate study data with the raw values of current and cumulative LED divided by the subject’s weight giving LED per kilo of body weight. In addition to confirming the reality of the artefact described above the results were very similar to those using the original values of LED, so we propose not to adjust for body weight in this prespecified supplementary analysis.

[name] (12/28/2018)

STEADY-PD III
Statistical Analysis Plan Summary of Changes

Statistical Analysis

Plan Version Date Summary of Changes

- 1-Sep-14 Original Version
- 6-Mar-15 Addition of Subgroup Analysis - Including Gender and Race/Ethnicity
- 6-Oct-15 Minor formatting changes, added power for selected secondary analyses and subgroup analyses.
- 16-Dec-15 Section D. Subgroup Analysis - Including Gender and Race/Ethnicity. Clarified the will NOT have enough power to detect treatment effects among subgroups.
- 1-Dec-17 Per DSMB meeting 11OCT2017, the interim and futility analysis will not be performed. Clarified in the plan.
- 28-Dec-18 Clarification to the SAP - Combining sites with low enrollment and influence of symptomatic medication of the primary outcome, section 4C.

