8 STATISTICAL CONSIDERATIONS

8.1 General Design Issues

The study is designed as a randomized Phase 3, 2-arm, double-blind, parallel group trial with subjects randomized to Isradipine IR 5 mg or matching placebo twice daily.

Primary efficacy analysis will be performed after all subjects complete 36 months on their randomized treatment assignment. We expect that nearly all subjects will require symptomatic therapy (e.g., levodopa or dopamine agonist) prior to the end of the 36

months study; if so they will still continue on their randomized treatment assignment in conjunction with the symptomatic therapy. In that case the primary statistical analysis will be based on UPDRS assessed in the medications ON state (based on the subject/ investigator defined BEST ON, approximately 1 hour after dose of symptomatic therapy).

Primary efficacy variable

The primary efficacy measure is the change in the total UPDRS score in the active treatment arm versus placebo between the baseline and 36 months. In order to provide assurance that any differences between the treatment groups in the primary outcome measure are not due to differences in the usages of symptomatic medication, current and cumulative dosages of symptomatic medication at the 36-month visit will also be compared, using accepted levodopa dose equivalency formulas[1] We will also repeat our UPDRS analyses after stratification by medication status (dosage of symptomatic treatment calculated as the levodopa equivalent dose). We will also perform exploratory analyses along the lines suggested by Holford and Nutt[56], based on flexible models of both short term symptomatic effects and long-term disease-modifying effects of treatment.

Secondary efficacy measure

The study secondary objectives are to explore long-term efficacy of Isradipine IR 5 mg twice daily to slow progression of disability between the baseline and 36 months of treatment as measured by parameters that reflect long term disability in PD:

- 1) Motor function (characterized by UPDRS Part III OFF score, UPDRS ambulatory capacity subscore, time to initiation of symptomatic therapy, time to onset of motor complications, dose and utilization of symptomatic therapy)
- 2) Cognitive function as measured by MoCA
- 3) Global measures of disability as measured by modified Rankin score
- 4) Measures of functional status and quality of life (PDQ-39, modified Schwab and England, MDS-UPDRS Motor and Non-Motor Experience of Daily Living)

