The key issues in the determination of sample size are the variability of the primary outcome measure and the magnitude of the treatment effect one wishes to detect.

As regards the former, there are several sources of data regarding changes in total UPDRS in untreated patients to a two, three or four year point, generally following introduction of symptomatic therapy. Published sources include the CALM-PD study [8] and the Swedish selegiline study [9]. Unpublished data are also available from a long-

term follow-up of patients originally enrolled in the PRECEPT study [2]. All these studies support a standard deviation of 12.0 units for the change in total UPDRS from baseline to 36 months. The same data suggest an average change in total UPDRS of around 4.0 points over this same time period. Of course this change is deceiving, as the change would likely be much greater in the absence of symptomatic treatment. If we assume that treatment with levodopa or a dopaminergic agonist provides a “bonus” of 12 points, then the underlying true decline in function over this period would be around 16 points, a value broadly consistent with the rate of change in total UPDRS in subjects prior to treatment. We have chosen to power our study to detect a four point effect, representing an overall 25% reduction in the underlying rate of progression. We believe that a difference of this magnitude would be sufficient to influence clinical practice and may suggest the likelihood of longer term benefit.

Using the above assumptions, a two-sided test with $\alpha = 0.05$ and $\beta = 0.8$ and making allowance for 15% dropouts the required sample size is 168 subjects per group or a total 336 subjects.

The Table below shows the effect of higher than expected withdrawal rates (20% and 25%) expressed in three alternative metrics (A) The power to detect a 4.0 point difference, (B) The effect size that would be detectable with 80% power and (C) the number of additional subjects that would need to be enrolled to maintain power at 80% to detect a 4.0 point difference.

| Overall Withdrawal Rate | Power (A) | Effect Size (B) | Additional Subjects (C) |
|-------------------------|-----------|-----------------|-------------------------|
| 15% | 80% | 4.0 pts. | 0 |
| 20% | 78% | 4.1 pts | 21 |
| 25% | 75% | 4.25 pts. | 45 |

Power for key secondary outcomes

We will also examine power for some key secondary outcomes of this study.

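### The blinded correction for symptomatic medication uses two linear dose terms and no on-therapy term, so it can be biased in either direction when the arms use therapy differently

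*SAP*

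**What the plan says.** SAP 4.C.III planned to add current levodopa-equivalent dose (LED) as a predictor, to see whether a primary difference could be put down to unequal use of symptomatic therapy. Clarification (2) withdraws that, because LED is a post-randomization variable, and substitutes a two-step method.

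First, the effects of current and cumulative LED are estimated on aggregate data before unblinding, "from a mixed model analysis using data from all study visits and which explicitly allows subjects to have differing underlying rates of disease progression". Second, "The estimated coefficients of the two LED variables (current and cumulative levodopa equivalent doses) will then be used to adjust each" subject's final UPDRS to the value projected without medication. The projected scores are then analysed with the primary model.

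The SAP says the type I error is correct under an overall null, defined as "no effect of isradipine relative to placebo on either disease progression or usage of symptomatic medication", and that this holds "irrespective of whether the relationship between these two outcome variables is modeled accurately". The one variant examined was LED per kilogram of body weight, which was dropped: "so we propose not to adjust for body weight in this prespecified supplementary analysis".

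Two other places bear on the form of the effect. SAP 7 (Power and Sample Size Considerations) reasons "If we assume that treatment with levodopa or a dopaminergic agonist provides a “bonus” of 12 points", giving an underlying decline of about 16 points. Protocol 8.1 promises exploratory analyses "based on flexible models of both short term symptomatic effects and long-term disease-modifying effects of treatment"; the SAP does not specify them.

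**The concern.** Two dose coefficients, applied as a linear correction through zero, are the whole adjustment. Any gain from starting therapy that does not scale with dose has to be absorbed by those coefficients. The current-LED coefficient is then wrong for between-arm dose differences, and the cumulative-LED term picks up an apparent worsening that partly offsets it. What is left enters the treatment contrast whenever the arms differ in use of therapy.

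That is the case the analysis exists to examine, and the type I error statement does not extend to it. Nearly all subjects are expected to need therapy by Month 36, so this analysis will be the natural reply when someone asks whether rescue medication explains the result. An error of a point or more is material against a 4-point target.

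**Working it through.** **Plan figures (SAP 7).**
- Sample size: 2 × (1.96 + 0.84)² × 12² / 4² gives 142 per arm; 142 / 0.85 gives 168 per arm, 336 in total, as stated.
- Completers: 336 × 0.85 / 2 = 142.8 per arm. Standard error: 12 × √(2/142.8) = 1.42.
- Detectable LED difference: 2.80 × 277 × √(2/142.8) = 91.8, stated as 92, which is 24% of the mean of 390.

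**Simulation.** 143 completers per arm, the protocol's in-person visits, a mean decline of 16 points and no isradipine effect on progression. Assumptions that are not in the documents: residual SD 5, slope SD 3 points per year, baseline SD 8.5, gamma-distributed doses (rising over 1.5 years, or constant) and a logistic start rule driven by observed worsening. Site was omitted.

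With equal use, the simulated trial resembled the plan: about 52% on therapy at Month 12 (Protocol 3.2: 50%), 92% at Month 36 (SAP 7: all but 10%), LED 393-407 with SD 273-279 (SAP 7: 390, 277), and change about 4.9 with SD about 11.1 (SAP 7: 4.0, 12.0).

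The pooled mixed model contained time, current LED and cumulative LED, with random intercept and slope. It was fitted by GLS with the true variance components, 400 runs per cell.

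**Decomposition.** Projected score = final score − b1 × current LED − b2 × cumulative LED. The projected arm difference (isradipine minus placebo; negative favours isradipine) is therefore the unadjusted difference − b1 × ΔLED − b2 × Δcumulative. For lower doses in the rising pattern, b1 = −3.11 per 100 units and ΔLED = 301 − 392 = −91. The current-LED part is −(−3.11)(−0.91) = −2.83. The projected change is −1.06 − 0.01 = −1.07, so the cumulative part is about +1.76. Other rows follow the same way.

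| True benefit; difference in use | Dose pattern | LED placebo / isradipine | Unadjusted | Current-LED part | Cumulative part | Projected | Rejection |
|---|---|---|---|---|---|---|---|
| Flat 12; none | rising | 393 / 395 | −0.07 | – | – | −0.03 | 4.8% |
| Flat 12; none | constant | 406 / 407 | +0.01 | – | – | +0.03 | 5.2% |
| Flat 12; lower doses | rising | 392 / 301 | +0.01 | −2.83 | +1.76 | −1.06 | 11.5% |
| Flat 12; lower doses | constant | 407 / 311 | −0.01 | −2.05 | +0.76 | −1.30 | 15.0% |
| Flat 12; higher doses | rising | 394 / 487 | +0.14 | +2.29 | −1.46 | +0.97 | 10.2% |
| Flat 12; higher doses | constant | 407 / 504 | −0.05 | +1.65 | −0.60 | +1.00 | 13.3% |
| Flat 12; fewer start | rising | 394 / 293 | +2.46 | −2.89 | +2.24 | +1.81 | 26.0% |
| Flat 12; fewer start | constant | 407 / 316 | +2.45 | −1.77 | +0.72 | +1.40 | 17.0% |
| Proportional to LED; lower doses | rising | 395 / 303 | +2.99 | −2.83 | −0.04 | +0.12 | 3.0% |
| Proportional to LED; lower doses | constant | 406 / 311 | +2.97 | −2.93 | −0.01 | +0.03 | 3.7% |

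In the fewer-start rows 72% of isradipine subjects are on therapy at Month 36, against 92-93% on placebo. The unadjusted +2.5 is what a flat benefit implies: 12 × (0.93 − 0.72) = 2.5.

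**Checks.**
- Monte Carlo error of a mean is about 11.1 × √(2/143) / √400 = 0.07 points.
- A REML fit (31-35 runs per cell) gave −1.1 (lower), +0.9 (higher) and 0.0 (equal).
- At the plan's standard error of 1.42, biases of −1.06 and −1.30 imply rejection of about 12% and 15%, as simulated.

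**Other inputs.** A second simulation, with 84% treated at Month 36, gave −1.0 to −1.3 (lower doses), +1.0 to +1.2 (higher) and +1.7 to +2.1 (fewer start, 55% v 84%). A saturating effect with lower doses gave −0.6 to −0.9. A third, with about 93% treated, gave −1.2 to −1.4 for a step and −0.7 to −0.9 for a saturating effect with lower doses. For higher doses and for fewer starters it gave +0.5 to +0.9 and +1.0 to +1.8, ranges that do not separate the two shapes.

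**With the indicator added to both LED terms.** The second simulation left at most 0.2 points of bias in every null scenario. The third left at most about 0.3.

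**The case against.** The best defence is that this is a supplementary analysis. The primary ANCOVA is not adjusted for medication, and arm differences in use are examined directly: proportion treated and current LED in SAP 4.A, and current and cumulative dose plus stratification by LED in Protocol 8.1. A 90-unit gap would be seen there. Nothing in the documents predicts such a gap: 92 units is a detectable difference, and the pilot trial in Protocol 2.6 found no evidence of a difference in need for therapy. All of that stands, and it limits the weight of the point. It does not supply a correct projection if use does differ.

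A reader might also infer more than the documents support:
- **That unequal dosing always yields a false benefit.** It does not. Higher doses, or fewer starters, give false harm. With fewer starters the projection still reduces the unadjusted distortion, from about +2.5 to between +1.4 and +1.8.
- **That SAP 7 contradicts the Clarification.** The 12 points are a group-level planning figure, and nothing there says they are independent of dose. They fit a linear effect of 12/390 = 3.1 points per 100 units, and under that form the planned projection is unbiased. A flat step is one possible reading.
- **That the type I error claim is wrong.** The condition of no effect on medication use is printed beside it, and rejection stayed near 5% under equal use. The sentence is correct but silent on unequal use.
- **That the bias approaches 92 × 12/390 = 2.8 points.** The cumulative-LED term cancels part of it.
- **That a true slowing is necessarily overstated.** That requires lower doses among treated isradipine subjects as well.

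**Conclusion.** The point holds as a functional-form weakness in a supplementary analysis. With no on-therapy term and no check of dose-response shape, the projection is unbiased under unequal use only if the benefit is linear in LED.

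Under a flat 12-point benefit, an LED difference of about 90 units and no progression effect, the bias is about −1.0 to −1.4 points with lower isradipine doses among treated subjects, about +0.9 to +1.2 with higher doses, and about +1.4 to +2.1 with fewer starters. A saturating effect gives smaller bias in the same directions. Against the 4-point target, the dose-difference cases amount to roughly a quarter to a third.

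The direction under each pattern was stable across simulations. The sizes were not exact: they depend on the assumed variance components, dose pattern and start rule, and one set of inputs gave somewhat smaller values for the two false-harm patterns. The rejection rates assume variability near the plan's SD of 12, which is for the observed change; the documents give none for the projected outcome. This is a cheap improvement, not an error that threatens the primary result.

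**What to change.** Before the blind is broken, amend Clarification (2) to include an indicator for being on any symptomatic therapy at the visit in the blinded mixed model, alongside current and cumulative LED, and to include its coefficient in the projection. Optionally, prespecify a saturating LED term as a sensitivity check.

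The indicator should be added to the LED terms and not replace them. When the benefit was proportional to LED and isradipine doses were 24% lower, an on/off term alone left a bias of about +3.0 points.

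The type I error sentence needs no correction. One added clause saying that the guarantee does not extend to unequal use of therapy would prevent misreading.

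The cost is one model term. The standard error rises by about 1% (at most 3% across the scenarios run), and by about 1% or less where the effect is truly linear. No new data are needed.
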